1 OVERVIEW

Study Title: Journey of Transformation

1.1 Home institution. Identify the institution through which the lead researcher listed on the IRB application will conduct the research. Provide any helpful explanatory information.

In general, the home institution is the institution (1) that provides the researcher's paycheck and that considers him/her to be a paid employee, or (2) at which the researcher is a matriculated student. Scholars, faculty, fellows, and students who are visiting the UW and who are the lead researcher: identify your home institution and describe the purpose and duration of your UW visit, as well as the UW department/center with which you are affiliated while at the UW.

Note that many UW clinical faculty members are paid employees of non-UW institutions.

The UW IRB provides IRB review and oversight for only those researchers who meet the criteria described in the [SOP Use of the UW IRB](#).

University of Washington

1.2 Consultation history. Has there been any consultation with someone at HSD about this study?

It is not necessary to obtain advance consultation. However, if advance consultation was obtained, answering this question will help ensure that the IRB is aware of and considers the advice and guidance provided in that consultation.

	No
	Yes

→ If yes, briefly describe the consultation: approximate date, with whom, and method (e.g., by email, phone call, in-person meeting).

[name] and [name] IRB Reliance Administrator
: Discussion around reliance and that this is a just-in-time, funder requested application

1.3 Similar and/or related studies. Are there any related IRB applications that provide context for the proposed activities?

Examples of studies for which there is likely to be a related IRB application: Using samples or data collected by another study; recruiting subjects from a registry established by a colleague's research activity; conducting Phase 2 of a multi-part project, or conducting a continuation of another study; serving as the data coordinating center for a multi-site study that includes a UW site.

Providing this information (if relevant) may significantly improve the efficiency and consistency of the IRB's review.

	No
	Yes

→ If yes, briefly describe the other studies or applications and how they relate to the proposed activities. If the other applications were reviewed by the UW IRB, please also provide: the UW IRB number, the study title, and the lead researcher's name.

--

1.4 Externally-imposed urgency or time deadlines. Are there any externally-imposed deadlines or urgency that affect the proposed activity?

HSD recognizes that everyone would like their IRB applications to be reviewed as quickly as possible. To ensure fairness, it is HSD policy to review applications in the order in which they are received. However, HSD will assign a higher priority to research with externally-imposed urgency that is beyond the control of the researcher. Researchers are encouraged to communicate as soon as possible with their HSD staff contact person when there is an urgent situation (in other words, before submitting the IRB application). Examples: a researcher plans to test an experimental vaccine that has just been developed for a newly emerging epidemic; a researcher has an unexpected opportunity to collect data from students when the end of the school year is only four weeks away.

HSD may ask for documentation of the externally-imposed urgency. A higher priority should not be requested to compensate for a researcher's failure to prepare an IRB application in a timely manner. Note that IRB review requires a certain minimum amount of time; without sufficient time, the IRB may not be able to review and approve an application by a deadline.

No

Yes

→ If yes, briefly describe the urgency or deadline as well as the reason for it.

NIH is ready to issue Notice of Award pending IRB determination. Our NIH project officer has requested we include our IRB determination with our just in time materials.

1.5 Objectives Using lay language, describe the purpose, specific aims, or objectives that will be met by this specific project. If hypotheses are being tested, describe them. You will be asked to describe the specific procedures in a later section.

If this application involves the use of a HUD "humanitarian" device: describe whether the use is for "on-label" clinical patient care, "off-label" clinical patient care, and/or research (collecting safety and/or effectiveness data).

To test the preliminary efficacy of the [REDACTED] Journey of Transformation–Native Youth Health Leadership Program (CHJ) which is an adapted and expanded version of the Discovering Our Story intervention curriculum, a 2010 SAMSHA-identified best practice AIAN strengths-based comprehensive substance use and health risk prevention and health leadership program for AIAN youth.

Outcomes:

- decrease rates of ATOD (marijuana and other drugs) use, intentions to use, susceptibility,
- increase refusal efficacy;
- decrease sexual activity (number of partners, condomless intercourse
- delay sexual initiation,
- increase sexual self-efficacy (i.e., refusal, avoidance), and safer sex intentions.

Examine how stressful life events, mental health (depression/anxiety/self-esteem), cultural protective (identity, enculturation, collectivist values, community connectedness, communal mastery, benevolence/traditionalism) and PYD-related factors (e.g., connectedness, efficacy, ATOD and sexual refusal) moderate or mediate the intervention's efficacy.

1.6 Study design. Provide a one-sentence description of the general study design and/or type of methodology.

Your answer will help HSD in assigning applications to reviewers and in managing workload. Examples: a longitudinal observational study; a double-blind, placebo-controlled randomized study; ethnographic interviews; web scraping from a convenience sample of blogs; medical record review; coordinating center for a multi-site study.

A randomized waitlist stepped wedge design with study participants recruited in staggered cohorts, with those in each annual recruitment wave receiving *individual-level random assignment* to either immediate intervention or waitlist control.

1.7 Intent. Check all the descriptors that apply to your activity. You must place an “X” in at least one box.

This question is essential for ensuring that your application is correctly reviewed. Please read each option carefully.

Descriptor
 1. Class project or other activity whose purpose is to provide an educational experience for the researcher (for example, to learn about the process or methods of doing research).
 2. Part of an institution, organization, or program’s own internal operational monitoring.
 3. Improve the quality of service provided by a specific institution, organization, or program.
 4. Designed to expand the knowledge base of a scientific discipline or other scholarly field of study, and produce results that: 
• Are expected to be applicable to a larger population beyond the site of data collection or the specific subjects studied, or• Are intended to be used to develop, test, or support theories, principles, and statements of relationships, or to inform policy beyond the study.
 5. Focus directly on the specific individuals about whom the information or biospecimens are collected through oral history, journalism, biography, or historical scholarship activities, to provide an accurate and evidence-based portrayal of the individuals.
 6. A quality improvement or program improvement activity conducted to improve the implementation (delivery or quality) of an accepted practice, or to collect data about the implementation of the practice for clinical, practical, or administrative purposes. This does not include the evaluation of the efficacy of different accepted practices, or a comparison of their efficacy.
 7. Public health surveillance activities conducted, requested, or authorized by a public health authority for the sole purpose of identifying or investigating potential public health signals or timely awareness and priority setting during a situation that threatens public health.
 8. Preliminary, exploratory, or research development activities (such as pilot and feasibility studies, or reliability/validation testing of a questionnaire)
 9. Expanded access use of a drug or device not yet approved for this purpose
 10. Use of a Humanitarian Use Device

11. Other. Explain:

1.8 Background, experience, and preliminary work. Answer this question only if the proposed activity has one or more of the following characteristics. The purpose of this question is to provide the IRB with information that is relevant to its risk/benefit analysis.

- Involves more than minimal risk (physical or non-physical)
- Is a clinical trial, or
- Involves having the subjects use a drug, biological, botanical, nutritional supplement, or medical device.

"Minimal risk" means that the probability and magnitude of harm or discomfort anticipated in the research are not greater than those ordinarily encountered in daily life or during the performance of routine physical or psychological examinations or tests.

a. **Background.** Provide the rationale and the scientific or scholarly background for the proposed activity, based on existing literature (or clinical knowledge). Describe the gaps in current knowledge that the project is intended to address.

This should be a plain language description. Do not provide scholarly citations. Limit your answer to less than one page, or refer to an attached document with background information that is no more than three pages long.

Study is a phase 2 clinical trial.

Evidence shows that Native Americans have high rates of substance use disorder (ATOD) over the lifetime and die at higher rates than non-Natives from ATOD-related diseases such as cirrhosis and suicide. They also have a higher prevalence of behavioral risk factors for substance misuse and sexual health risk. **AIAN youth are at the heart of this health crisis.** AIAN youth have a lower overall mean age of tobacco use, alcohol use, and marijuana initiation (11.5 years) than the general population. Early initiation of ATOD use is associated with an array of negative physical and behavioral health outcomes including academic challenges, later ATOD abuse, and early sexual initiation. AIAN youth also have the earliest age of first sexual intercourse, and have more sexual partners than their non-AIAN counterparts. To stem the epidemic of ATOD-SRH-related health disparities among AIAN youth, collaborative partnerships must focus on development of culturally grounded, sustainable health interventions that incorporate healing related to historical trauma. In response, we will adapt and expand a promising Native-specific intervention, Discovering Our Story, **to develop the [REDACTED] Journey of Transformation (CJT) - Native Health Youth Leadership Program**, an intervention to prevent ATOD use and SRH in AIAN youth attending boarding school. If successful, this project would have high relevance for boarding and tribal day school students across the country.

This research will fill an immediate gap in the substance use and sexual health risk (ATOD-SRH) prevention literature and policy given the dire need for empirical research to document a culturally relevant and comprehensive ATOD-SRH health promotion model. Data on the feasibility, acceptability, and efficacy of a youth health leadership intervention among ATOD-SRH risk AIAN youth would be a significant contribution to the substance abuse and sexual and reproductive health fields for AIANs as well as other groups. The data obtained in this study will form the basis for future large-scale efficacy studies with multiple tribal groups. The proposed work will make several distinctive contributions, including: (1) being the first ATOD-SRH study conducted at an Indian boarding school; (2) being the first study that specifically theorizes the role of trauma on ATOD-SRH risk outcomes among AIAN youth; (4) using an Indigenist theoretical model

and empirical measures that capture specific culturally-based factors such as historical trauma and community connectedness; (5) focusing on ATOD- SHR prevention issues among AIAN youth, a group at high risk for ATOD- SRH health disparities; (4) incorporating some of the same measures (behavioral) used in Strong Heart Study, Circle of Life HIV prevention among AIAN youth; and (5) incorporating an interdisciplinary and intertribal team approach with American Indian community members, leaders, and elders. Additionally, the project is significant because it builds upon an established relationship with a Native organization and is geared toward continued development of the research infrastructure and health treatment capacity.

Given the health risks to this population and the scarcity of research focused on their needs, combined with the potential risks to participants and the anticipated benefits to public and AIAN health, the proposed research and its potential risks are considered reasonable by the investigative team.

b. Experience and preliminary work. Briefly describe experience or preliminary work or data (if any) that you, your team, or your collaborators/co-investigators have that supports the feasibility and/or safety of this study.

It is not necessary to summarize all discussion that has led to the development of the study protocol. The IRB is interested only in short summaries about experiences or preliminary work that suggest the study is feasible and that risks are reasonable relative to the benefits. Examples: Your team has already conducted a Phase 1 study of an experimental drug which supports the Phase 2 study being proposed in this application; your team has already done a small pilot study showing that the reading skills intervention described in this application is feasible in an after-school program with classroom aides; your team has experience with the type of surgery that is required to implant the study device; the study coordinator is experienced in working with subjects who have significant cognitive impairment.

This research will be conducted by PI [name] (enrolled Snohomish Tribe) and co-I [name] (enrolled Choctaw Nation) who co-direct the Indigenous Wellness Research Institute (IWRI). They are highly experienced indigenous researchers who have conducted intervention research in Native communities for the last 15-20 years respectively serving as PI or Co-PI on over 30 federally-funded studies with tribal communities and/or Native organizations. The [REDACTED] intervention team, lead By [REDACTED], has extensive expertise in conducting school-based interventions with Native youth. [REDACTED] and her team have worked extensively with middle and high school students including several projects with [REDACTED] students.

The study builds on preliminary research from Drs [name] and [name]:

Preliminary Feasibility, Acceptability, and Efficacy of an AIAN-based MI Intervention. Drs. [name] and [name] in partnership with the Tulalip Tribes completed a 12-month intervention that had a culturally tailored, 5-session MI-based CVD prevention component (həli?dxʷ Project; aka Healthy Hearts- U01HL087322-05). The project successfully culturally adapted MI for CVD prevention, trained AIANs to implement the intervention, and conducted a preliminary feasibility and efficacy trial. Initial results indicated that participants enthusiastically embraced the MI component. Findings indicate that participants that completed all MI sessions engaged in more moderate intensity exercise greater than 30 minutes, maintained at 12-month follow-up; and that greater MI attendance was significantly associated with enhanced CVD health.

Yappalli study (NIDA RO1 DA037176). Yappalli is an experiential, outdoor-based 3-month (with a 10 day walk on the Trail of Tears) substance abuse-obesity prevention RCT targeting at-risk adult Choctaw women. However, findings from two separate qualitative studies- have been completed to date- (study 1) analysis drew on two sources of qualitative data from Choctaw tribal members: 14 semi-structured interviews and two focus groups (N=9) and study 2 analysis drew on 35 Yappalli participants who had completed the intervention. Qualitative data suggests that inclusion of a culturally-tailored IMB approach and culturally derived health promotion model helped our participants begin working toward individualized

Discovery our story (DOS) pilots and evaluation. Led by [REDACTED], the DOS is recognized by SAMHSA CDC as a best practice intervention to develop an age-appropriate middle-school age DOS curriculum. As part of the study, focus group sessions were held over three years at partner locations seeking feedback from Portland's AIAN community. The DOS curriculum originally focused on four primary areas: addictions, diabetes prevention, domestic violence, and mental health prevention. Pilot results indicated that the intervention: connected participants to culture and knowledge; instigated memories of teachings of relatives; identified positive behavioral actions; and provided hope and practical strategies for healthful living. The efficacy of storytelling as a teaching method was one of the strongest findings.

This study will be monitored in compliance with a Data Safety and Monitoring board.

1.9 Supplements. Check all boxes that apply, to identify relevant Supplements that should be completed and uploaded to **Zipline**.

This section is here instead of at the end of the form to reduce the risk of duplicating information in this IRB Protocol form that you will need to provide in these Supplements.

Check all That Apply	Type of Research	Supplement Name
	Department of Defense The research involves Department of Defense funding, facilities, data, or personnel.	SUPPLEMENT Department of Defense
	Department of Energy The research involves Department of Energy funding, facilities, data, or personnel.	SUPPLEMENT Department of Energy
	Drug, biologic, botanical, supplement Procedures involve the use of any drug, biologic, botanical or supplement, even if the item is not the focus of the proposed research	SUPPLEMENT Drugs
	Emergency exception to informed consent Research that requires this special consent waiver for research involving more than minimal risk	SUPPLEMENT Exception from Informed Consent for Emergency Research (EFIC)
	Genomic data sharing Genomic data are being collected and will be deposited in an external database (such as the NIH dbGaP database) for sharing with other researchers, and the UW is being asked to provide the required certification or to ensure that the consent forms can be certified	SUPPLEMENT Genomic Data Sharing
	Medical device Procedures involve the use of any medical device, even if the device is not the focus of the proposed research, except when the device is FDA-approved and is being used through a clinical facility in the manner for which it is approved	SUPPLEMENT Devices
	Multi-site or collaborative study The UW IRB is being asked to review on behalf of one or more non-UW institutions in a multi-site or collaborative study.	SUPPLEMENT Multi-site or Collaborative Research
		SUPPLEMENT Non-UW Individual Investigators

Document Date & Version

01/21/2021
Version 3.0

Researcher Date & Version

10/04/2022
Version 5.1
Page 7 of 56

Non-UW Individual Investigators

The UW IRB is being asked to review on behalf of one or more non-UW individuals who are not affiliated with another organization for the purpose of the research.

Other REDCap Installation Attestation for Electronic Consent

The research will use a non-UW installation of REDCap for conducting and/or documenting informed consent.

[SUPPLEMENT Other REDCap Installation](#)

None of the above

1.10 **Confirm by checking the box below** that you will comply with these basic COVID infection and risk control measures, OR that you have an exception granted by the HSD Director: (a) the only in-person interactions are essential for the study; (b) study team members and participants will wear face coverings throughout all procedures; (c) all study staff and participants will be screened for COVID-19 just prior to each research visit; and (d) no participants over the age of 85 years will be enrolled if their in-person participation is not connected with a clinical visit. See this [webpage](#) for details, including what “screening” means.

Review the [HSD website](#) for current guidelines about which in-person research activities are allowable.

Confirmed

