Because this project has been discontinued for this year, we are paying enrolled participants for completing the baseline assessment. We've been asked by the school principal to pay students who have finished the first survey since they will not go through the intervention or have the opportunity to take future surveys, and therefore receive compensation. The amount would be a \$20 online gift card, which is what they would be paid for the first follow-up assessment.

4.5 Non-monetary compensation. Describe any non-monetary compensation that will be provided. Example: extra credit for students; a toy for a child. If class credit will be offered to students, there must be an alternate way for the students to earn the extra credit without participating in the research.

All youth in the class will receive project t-shirts, culturally relevant study posters, pens, writing pads, and water bottles for participation.

4.6 Will data or specimens be accessed or obtained for recruiting and screening procedures prior to enrollment?

Examples: names and contact information; the information gathered from records that were screened; results of screening questionnaires or screening blood tests; Protected Health Information (PHI) from screening medical records to identify possible subjects.

→ If no, skip the rest of this section; go to [question 5.1](#).

→ If yes, describe the data and/or specimens (including PHI) and whether it will be retained as part of the study data.

4.7 Consent for recruiting and screening. Will consent be obtained for any of the recruiting and screening procedures? ([Section 8: Consent of Adults](#) asks about consent for the main study procedures).

"Consent" includes: consent from individuals for their own participation; parental permission; assent from children; consent from a legally authorized representative for adult individuals who are unable to provide consent.

Examples:

- For a study in which names and contact information will be obtained from a registry: the registry should have consent from the registry participants to release their names and contact information to researchers.
- For a study in which possible subjects are identified by screening records: there will be no consent process.
- For a study in which individuals respond to an announcement and call into a study phone line: the study team person talking to the individual may obtain non-written consent to ask eligibility questions over the phone.

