At the orientation meeting, a study package will be handed to each youth. The package will include Native items such as sage or lavender, a writing pad and pen and pencil with a Native design and study phone number, two copies of the assent form (one for them to sign and the other to keep as their copy), and the study flyer. UW and [REDACTED] staff will inform the students about the research project, highlighting that it is

completely voluntary and then review the assent form and ask for questions. At the end of the meeting, students will be instructed to write their names on the assent form and indicate if they are interested in participating in the project (Yes/No) or would like more information. Students who are interested in participating will also be asked to fill out a contact information sheet, which asks for their name(s), birth date, preferred pronouns, email address, phone number, and space to provide any additional contact information (ex., social media). If they would like more information, they will be asked to provide contact information (similar to that of those who have assented) and a UW staff person will contact them. They will be informed that they may also reach out to the UW or [REDACTED] staff at any time before the first day of class (within the two weeks) if they have any additional questions about participation.

Students will hand in one signed copy of the assent form when they exit the room.

UW or [REDACTED] staff will then follow-up with students that indicated they are interested in participating and welcome them to the program and asked if they have any additional questions. They will also follow-up with students who request additional information.

For students that have indicated they are interested, they will be randomly assigned to a class offering the intervention sessions. Some classes will start the intervention curriculum in the Fall, others in the Spring. Students that indicated they are not interested they will be assigned to a class that is not participating in the intervention curriculum. This is easily done as there are multiple classes for each grade.

Students may choose to drop out of the research program by notifying research staff by email and reassignment to a health class will be provided. As standard practice, students periodically change class assignments so this would not seem out of the norm.

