Journey of Transformation Curriculum for Native American Adolescents (JOT)

NCT05274217

[name]

Statistical Analysis Plan

IRB Approved 03-16-2021

Statistical Design and Power

This study will evaluate the following primary outcomes: (1) alcohol, tobacco, and other drugs (ATOD; intentions to use, overall use, susceptibility, refusal self-efficacy) and (2) sexual and reproductive health (sexual activity, sexual self-efficacy, safer sex intentions). An intent-to-treat approach will be used to estimate the magnitude and statistical significance of intervention effects at immediate post-intervention. Each outcome will be evaluated in a separate generalized linear mixed model to evaluate the effect of CHJOT curriculum on intervention outcomes. Continuous outcomes will be modeled using a Gaussian link function for normally distributed data and binary outcomes using a logit link for Bernoulli-distributed data. The following equation represents the basic model for the outcomes: $Outcome_{tij} = b_0 + b_1 Intervention_i + b_2 Time + b_3 (Intervention_{ij} \times Time_{tij}) + u_{0i} + r_{0ij} + e_{tij}$, where t indexes assessment, i indexes individual, and j indexes classroom. The last three terms on the right side of the model equation represent the variability between classrooms (u_{0i}), between individuals within classroom (r_{0ij}), and residual error (e_{tij}), respectively. The statistical test of the CHJOT curriculum will be the Intervention by Time interaction, which will evaluate whether recipients of the intervention curriculum improved more or decreased less from pre- to 2-month post-intervention compared with waitlist control.

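### Randomisation is within annual recruitment waves, but the primary model has no wave or wave-by-time term and no allocation ratio per wave is stated

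*Protocol*

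**What the plan says.** Protocol 1.6 (Study design) describes "study participants recruited in staggered cohorts", "with those in each annual recruitment wave receiving" individual-level assignment to one of the two arms. The annual wave is therefore a stratum of the randomisation. Neither document states the number of waves or the allocation ratio.

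The SAP (Statistical Design and Power) gives one model: "The following equation represents the basic model for the outcomes". Its fixed terms are intervention (b1), time (b2) and their product (b3). Its indices are given as "where t indexes assessment, i indexes individual, and j indexes classroom". On the random part it says "The last three terms on the right side of the model equation represent the variability between classrooms", then between students within classroom, then residual error. There is no random slope for time. The test is defined as follows: "The statistical test of the CHJOT curriculum will be the Intervention by Time interaction".

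On how the arms are filled, Protocol 7.2 (Assent process) says that interested students are randomly assigned to a class, and adds: "Some classes will start the intervention curriculum in the Fall, others in the Spring".

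**The concern.** An analysis should normally carry the factors by which the trial was randomised. Here the factor is the recruitment year, and ninth-grade cohorts a year apart can differ in two ways.

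They can differ in level, for example in how many students already use alcohol at entry. This does little harm: a level difference cancels from each student's change, and the classroom and student intercepts take it up.

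They can also differ in background change over the months between assessments. No term in the model takes this up. It stays in the error of b3, which is itself a difference in change. If, in addition, the share of students sent to the immediate arm differs from year to year, the years are mixed in different proportions in the two arms, and part of the year effect is read as an intervention effect. At stake are a little precision in the first case and some bias in the estimate in the second.

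**Working it through.** **Inputs from the SAP:** pre-post correlation r = 0.25; 216 students analysed; effect after the contamination allowance d = 0.20; type I error 5% (taken as two-sided, since the SAP does not say). **Assumptions, because the documents give no figures:** outcome SD of 1 at each assessment, equal arms overall, no clustering in the standard error, two equal waves, and the allocation splits and differences in change shown below. The SAP states no figure on this point to reproduce.

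**1. Standard error of b3.** Variance of change = 2(1 − 0.25) = 1.5. SE = √1.5 × √(4/216) = 0.167.

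**2. Constant allocation ratio.** Each wave then has the same expected weight in both arms, so the bias is zero. Variation between waves adds to the variance of change:

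| Between-wave SD of change (assumed) | SE ratio = √((1.5 + SD²)/1.5) | Loss |
|---|---|---|
| 0.1 | √(1.51/1.5) | 0.3% |
| 0.2 | √(1.54/1.5) | 1.3% |
| 0.3 | √(1.59/1.5) | 3.0% |

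**3. Ratio that varies by wave.** With complete pre and post data and no wave term, b3 is the raw difference in mean change, so

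bias = Σ over waves of (wave's background change) × (wave's share of the intervention arm − its share of the control arm).

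With two equal waves at 60:40 and 40:60, the first wave makes up 0.6 of the intervention arm and 0.4 of the control arm, so bias = difference in change × 0.2.

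| Difference in change (assumed) | Bias | Share of d = 0.20 | Bias/SE | Two-sided type I error |
|---|---|---|---|---|
| 0.1 SD | 0.02 | 10% | 0.12 | 5.2% |
| 0.2 SD | 0.04 | 20% | 0.24 | 5.7% |
| 0.3 SD | 0.06 | 30% | 0.36 | 6.5% |

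The last column is Φ(−1.96 − z) + Φ(−1.96 + z), with z = bias/SE.

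**4. Sensitivity to the assumed pattern.** For three equal waves with change drifting 0.2 SD per year (0.4 SD from first to last), the same formula gives 0 at 50/50/50% allocated to intervention, 0.027 at 45/50/55%, 0.053 at 40/50/60% and 0.089 at 33/50/67%. At 0.3 SD per year the last figure becomes 0.133. The answer depends wholly on what is assumed.

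**5. Which term is needed.** A wave main effect shifts both assessments of a student equally and drops out of the change, so adding it alone leaves the bias in place. Wave-by-time removes it. In simulated complete-data trials (three waves of 72, 40/50/60% allocation, drift 0.2 SD per year, true b3 = 0.20), mean b3 was 0.252 without wave terms and 0.198 with wave-specific change.

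**6. Binary outcomes.** The SAP's logit model has a random intercept per student. I fitted such a model to exact expected cell probabilities for two waves at 60:40 and 40:60 (intercept SD 1.5 assumed), leaving out a wave main effect of 0.5 to 1.5 logits. The shift went into b1, and b3 moved by less than 0.0002 logits. In the logit models too, only differences in change matter.

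**The case against.** The strongest reply is that the bias needs two things together, a ratio that varies by year and background change that differs by year, and the documents show neither. This stands. Protocol 7.2 says that classes start in different terms. It gives no class counts and does not say that the split changes from year to year. An unstated ratio is a gap in the documentation, not evidence of imbalance, and chance imbalance around a constant ratio does not bias b3.

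The size is also modest against the noise. Quoting 10% to 30% of d makes the bias look larger than it does beside a standard error of 0.167.

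Three stronger readings are tempting and should not be drawn:

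- A reader might infer that leaving out the wave main effect biases b3 in the logit models. That would be a worry in a marginal logit model. The SAP specifies a mixed model with student intercepts, where the effect is negligible (step 6).
- A reader might take the discontinued year in Protocol 4.4 ("Because this project has been discontinued for this year, we are paying enrolled participants for completing the baseline assessment") as a sign of uneven allocation. Those students receive no intervention and no further surveys, so they contribute no observed change in either arm, and the passage is silent on allocation.
- A reader might conclude that the primary result will be biased. The documents support only the conditional statement.

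Finally, the SAP calls its equation basic, so wave terms may not have been deliberately excluded. But it names no further covariates, so they are not pre-specified either.

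**Conclusion.** The omission is real, and worth correcting because the correction is cheap. It is not a serious threat to the trial as documented. With a constant ratio, b3 is unbiased and the price is a standard error 0.3% to 3% larger than needed, for an assumed between-wave SD of change of 0.1 to 0.3. With a varying ratio, the two-wave example gives a bias of 0.02 to 0.06 SD (0.12 to 0.36 SE) and a type I error of about 5.2% to 6.5%. More extreme assumed patterns give more. Which case applies cannot be settled from the documents, because the ratio per wave is missing.

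**What to change.** - Add wave and wave-by-time as fixed effects to every primary model, so that the analysis follows the randomisation. A wave main effect alone is not enough.
- State the allocation ratio for each wave and whether it is held constant.
- Define wave. Protocol 1.6 uses it for the yearly intake, while Protocol 7.6 uses second wave for the group that starts in spring. The model term must mean the yearly intake.

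The cost is SAP wording and about two degrees of freedom per added wave, which is small with 216 students analysed. The one real drawback is in the logit models: where a binary outcome is rare, few events per wave and assessment could make the fit unstable. The SAP should say in advance what will be done if such a model does not converge. All of this should be fixed before outcome data are examined, so that including wave does not become a data-driven choice.
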